Crohn's disease (CD) is a type of inflammatory bowel disease (IBD) characterized by chronic inflammation in the digestive tract. The pathogenesis of IBD involves immunological, genetic and environmental factors. Currently there is no cure for Crohn's disease and available medical and surgical treatments are expensive and often associated with significant side effects. Anti-tumor necrosis factor alpha (anti-TNF- α) agents are widely used for treatment of Crohn's disease. Electrical neuromodulation is a new treatment approach of bioelectronic medicine, involving molecular medicine, neuroscience, and bioengineering. Multiple possible mechanisms have been proposed for electrical neuromodulation in GI diseases, including central, autonomic, and/or enteric mechanisms. Vagal tone is significantly blunted in IBD and is associated with high TNF- α levels. Animal and preliminary human studies have demonstrated that electrical vagal nerve stimulation (VNS), including non-invasive vagal stimulation (nVNS), exerts an anti-inflammatory effect by harnessing the cholinergic anti-inflammatory pathway. In healthy humans nVNS has been shown to decrease tumor necrosis factor- α levels. Invasive VNS has been shown to improve inflammation in preliminary studies in patients with Crohn's disease.

Study Design: Single center open label interventional pilot study.

Estimated Enrollment: 12 participants

Aim: To assess the safety and efficacy of transcutaneous vagal stimulation in adult patients with active Crohn's disease.

Hypothesis: Non-Invasive VNS will decrease inflammation in people with Crohn's disease leading to decrease in inflammatory markers and symptoms of disease.

Outcome Measures:

Primary Outcome Measure:

1. Change in fecal calprotectin over time [16 weeks]

Secondary Outcome Measures:

1. Change in Crohn's disease activity index (CDAI) over time [16 weeks].
2. Change in serum cytokine levels over time [16 weeks]. Cytokine levels within the blood will be assessed and compared to baseline levels. The cytokines being assayed include C- reactive protein, tumor necrosis factor-alpha, Interferon-gamma, Transforming Growth Factor-beta and Interleukins (IL) - 1, 6, 10, 12, 17, 21, 23.
3. Heart Rate Variability (HRV) [Time Frame: 16 weeks]. Evaluating change in HRV from baseline until study completion.
4. Insulin levels will be collected and analyzed to see if there are any insulin changes before and after first stimulation

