2. Stool sample for the week 8 visit can be collected and sent to the IU Health pathology lab by the subject. Request for the stool sample collection will be provided to the subject at the baseline visit. Stool for week 8 can be collected within a week of Visit 3 (Week 8 +/- 1 week)
3. Subjects will complete a CDAl diary for each week. During weeks 1-7 to be collected at Visit 3 (Week 8 +/- 1 week).

Visit 3 (8 week or 56 days +/- 5 days)

1. Subject will take one set of two stimulations during the visit to verify compliance and appropriate use of the device.
2. Subjects will complete the Short Inflammatory Bowel Disease Questionnaire (SIBDQ).
3. Blood (29 ml/2 tablespoons) is collected for the inflammatory markers, cytokine levels, and serum samples for future analysis.
4. ECG electrodes are placed on the chest for measurement of the electrocardiogram (ECG)
5. The gammacore device will be placed on the left side of the neck in line with the vagus nerve. Electrical stimulations are applied using the device for 120 seconds followed by another 120 seconds after a 60 second pause. During this time the ECG recordings will continue.
6. After the stimulation period has ended, the subject will continue to be monitored and after 20 minutes post stimulation subject will be allowed to go home.
7. The subject will be asked to continue applying one set of 2 consecutive stimuli, lasting 120 seconds each, 3 times a day till the next visit in 8 weeks.

(Week 8-week 15)

1. Subjects continue to stimulate the left vagus nerve with one set of two stimulations, 120 seconds each, 3 times a day, one in the morning after waking up, one in the afternoon after lunch and one an hour before going to bed.

2. Stool sample for the week 16 visit can be collected and sent to the IU Health pathology lab by the subject. Request for the stool sample collection will be provided to the subject at the week 8 visit. Stool for week 16 can be collected within a week of Visit 4 (Week 16 +/- 1week)
3. Subjects will complete a CDAI diary for each week. During weeks 8-15 to be collected at Visit 4 (Week 16 +/- 1week).

Visit 4 (16 week or 112 days +/- 5 days)

1. Subject will take one set of two stimulations during the visit to verify compliance and appropriate use of the device.
2. Subjects will complete the Short Inflammatory Bowel Disease Questionnaire (SIBDQ).
3. Blood (29 ml/2 tablespoons) is collected for the inflammatory markers, cytokine levels, and serum samples for future analysis.

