4. ECG electrodes are placed on the chest for measurement of the electrocardiogram (ECG)
5. The gammacore device will be placed on the left side of the neck in line with the vagus nerve. Electrical stimulations are applied using the device for 120 seconds followed by another 120 seconds. During this time the ECG recordings will continue.
6. After the stimulation period has ended, the subject will continue to be monitored and after 20 minutes post stimulation subject will be allowed to go home.
7. The subject will be asked to return the device at the end of the visit.

Safety/Risk:

1. Non-invasive vagus nerve stimulation with Gammacore device may cause device-related adverse events (AEs) including:
 - Discomfort at the application site
 - Redness or irritation at the application site
 - Pain at the application site
 - Pain in the face/head/neck area (including toothache)
 - Muscle twitching and/or contractions in the face/head/neck area
 - Dizziness
 - Headache/migraine

- Facial Drooping and/or lip pull
 - Tingling, pricking, or a feeling of “pins and needles” on the skin where the device is applied (paresthesia/dysesthesia).
 - Coughing
 - Gastrointestinal discomfort
 - Headache
 - Hoarseness or change in voice
 - Irregular heartbeat (arrhythmia)
 - Light-headedness/dizziness
 - Metallic taste
 - Muscle twitching and or contractions of head/neck/face
 - Nausea
 - Pain
 - Shortness of breath (dyspnea)
 - Skin irritation
2. Tingling, pricking, or a feeling of “pins and needles” (paresthesia/dysethesia) the patient may experience discomfort, pain, bruising, swelling, blood clot formation, and very rarely infection at the site where the skin is punctured by the needle. Patient may also experience dizziness, nausea or fainting during the blood draw. The procedure is performed under aseptic conditions.
 3. There may be slight discomfort and irritation at the site of the ECG electrode placement. The patient might experience itching, redness, and skin irritation. There might be a slight sting for a few seconds when the electrodes are removed.
 4. Subjects may feel discomfort completing the CDAI diary, during answering the SIBDQ questionnaires or collecting stool samples.
 5. Potential loss of confidentiality. This is explained further under “Privacy/Confidentiality Issues” below.

Data Safety Monitoring:

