This study may be terminated by the investigators or the treating physician if they feel that it is no longer safe for a specific patient to participate. The termination will be documented by the investigator to indicate that the subject was withdrawn from the study and reason the subject was withdrawn.

If a subject experience a Crohn's disease flare they will be withdrawn from the study and considered a non-responder. If the subject changes their Crohn's disease medication they will be withdrawn from the study.

Privacy/Confidentiality Issues:

Participation in this study may cause a loss of privacy. To minimize this risk, the following steps will be implemented. All the subject's personal and medical data will be considered confidential to the extent allowed by law and therefore every effort will be made to keep all information strictly confidential. Only authorized personnel will have access to the samples, databases, and results. People who may review the information include the investigators, study staff, study monitors and the IUPUI Institutional Review Board or its designees. In addition, personal information may be disclosed if required by law. The samples collected from this study will be deidentified prior to being sent to the testing lab. The samples will be labeled with a code and not with the subject's name. All subject information will be stored in locked cabinets and on the principle investigator's and research coordinator's computers that are password protected. When the study is published, no subject names will be used.

Follow-up and Record Retention:

Research records, including signed informed consent documents, signed release of health information authorization forms and other documents that will facilitate reconstruction of study events by the IRB if necessary, will be stored for 7 years after the study or otherwise as required by Indiana law.

Additional Research Collection

An extra serum sample will be collected at each blood draw (15ml/ 1 tablespoon) and kept for future analysis under this protocol or in a similar protocol. The samples will be de-identified and stored at Indiana University Health University Hospital, Indianapolis, IN.

The manager of these samples will ensure they are properly used throughout their usable life and will destroy the samples at the end of the scheduled storage period, no longer than 15 years after the end of the study or the maximum allowed by applicable law. De-identified samples may be

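### The week 16 stool, which supplies the primary outcome, may be collected after the device has been handed back

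*Protocol*

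**What the plan says.** The Protocol names the primary outcome as "Change in fecal calprotectin over time [16 weeks" (Primary Outcome Measure). Four places settle when the last stool is taken and whether the subject is still on treatment:

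- Weeks 8–15 section, item 2: "Stool for week 16 can be collected within a week of Visit 4 (Week 16 +/- 1week".
- Visit 4 heading: "Visit 4 (16 week or 112 days +/- 5 days".
- Visit 3, item 7, on home stimulation: "3 times a day till the next visit in 8 weeks".
- Visit 4, item 7: "The subject will be asked to return the device at the end of the visit".

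The week 8 stool has the same kind of window, "Stool for week 8 can be collected within a week of Visit 3 (Week 8 +/- 1 week", but the subject leaves Visit 3 with the device and goes on stimulating. Week 16 blood and ECG are taken at Visit 4 itself, and the symptom diaries cover weeks 8–15. Under Study Withdrawal/Discontinuation, a Crohn's flare means withdrawal and non-responder status. A treatment change also ends participation: "If the subject changes their Crohn's disease medication they will be withdrawn from the study". No visit is scheduled after Visit 4.

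**The concern.** The same tolerance is used at weeks 8 and 16, but treatment continues through only the first of them. At week 16 the late half of the window falls after the device has gone back. No sentence requires the stool before device return, and none provides for stimulation after it. Of the week 16 measures, only the primary one can fall off treatment.

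The resulting week 16 change could mix on-device and off-device values among 12 subjects, with no control arm sharing the same timing. If the effect fades once stimulation stops, the fall in calprotectin is understated. If Crohn's treatment is stepped up after the last visit and before a late stool, the fall can be overstated, and no listed contact would record the change. An off-treatment stool also no longer lines up with the week 8 stool, or with the week 16 blood and the weeks 8–15 diaries, all of which are on treatment.

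**Working it through.** The protocol states no figure of its own to reproduce here. The check is arithmetic on the stated windows.

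**Inputs (Protocol)**

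- Visit 4 on day v, with v = 112 ± 5, so v runs from 107 to 117.
- Week 16 stool: within 7 days of Visit 4, and also described as week 16 ± 1 week, i.e. day 112 ± 7 = days 105 to 119.
- Stimulation: 3 sets a day, up to Visit 4.
- Device returned at the end of Visit 4.
- Enrolment: 12.

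**Longest time off device before the stool**

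The stool line gives two anchors. Counted from the visit, the latest stool is day v + 7, so the gap is 7 days whatever v is. Counted from nominal week 16, the latest stool is day 119, so the gap is 119 − v. If both limits bind, the gap is the smaller of the two.

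| Visit 4 on day | Visit anchor | Week 16 anchor | Both limits |
|---|---|---|---|
| 107 | 7 | 119 − 107 = 12 | 7 |
| 112 | 7 | 119 − 112 = 7 | 7 |
| 117 | 7 | 119 − 117 = 2 | 2 |

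Every reading allows an off-device sample on every permitted visit day. In prescribed sets not given, 7 days is 7 × 3 = 21 and 12 days is 12 × 3 = 36. The two anchors agree only at v = 112.

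**Share of the window after device return, v = 112**

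Days 113–119 out of days 105–119: 7 / (119 − 105 + 1) = 7/15 = 47%.

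**Week 8 for comparison**

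The device is kept, so the gap is 0 days in every case.

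**Possible effect on the mean change (assumed inputs)**

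The protocol does not say how fast calprotectin moves after stimulation stops. Let p be the share of subjects with a late stool and r the fraction of their fall lost by then. If late samplers would otherwise have had the same mean fall as the rest, the mean change from baseline to week 16 shrinks by p × r.

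| p | r = 0 | r = 0.25 | r = 0.5 | r = 1 |
|---|---|---|---|---|
| 3/12 = 0.25 | 0% | 6% | 13% | 25% |
| 7/15 = 0.467 | 0% | 12% | 23% | 47% |

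For example, 0.25 × 0.5 = 0.125 and 0.467 × 0.5 = 0.233. The value 3/12 is illustrative. The value 7/15 supposes stools spread evenly over the window with Visit 4 on day 112. Both p and r are assumptions.

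**Clerical mismatch**

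The diary item for the second period reads "During weeks 8-15 to be collected at Visit 4 (Week 16 +/- 1week", against ± 5 days in the Visit 4 heading, and Visit 3 has the same discrepancy. The two versions differ only on days 49–50, 62–63, 105–106 and 118–119. This has no bearing on the main point.

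**The case against.** The strongest reply is that collection before the visit was clearly expected. The stool item sits in the home-stimulation section, the sample is described as being for the week 16 visit, and the request is handed out eight weeks ahead. The late side of the window then looks like tolerance for stragglers, and an even spread over the window (p = 7/15) is unlikely. That is a fair reading of intent, and it makes the lower row of the shrinkage table an upper-end case. It does not change what the text allows.

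The 12-day gap needs the calendar anchor alone, a visit on the earliest permitted day and a stool on the last. If both limits bind, the maximum is 7 days. This also stands, so 7 days is the figure to carry.

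The primary outcome is worded as change over time, so the week 8 stool may also enter the analysis. That sample is always on treatment, and the p × r figures apply only to the change from baseline to week 16.

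The medication route needs a treatment change within days of the last visit, in subjects whose treatment was not expected to be increased at entry (exclusion criterion 1). It is possible rather than likely.

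Finally, how such samples are analysed may be left to a statistical analysis plan. When the specimen is taken and when the device goes back are protocol procedures, however, and no later analysis turns an off-treatment stool into an on-treatment one.

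**Conclusion.** The concern holds. As written, the final calprotectin value can be an off-treatment one: up to 7 days after device return when the window is counted from the visit, and up to 12 days on the least favourable reading. The day counts follow from the protocol alone. The size of any bias does not, because it depends on how many subjects sample late and how quickly the effect fades, neither of which is given. Over the assumed ranges the week 16 change shrinks by anything from 0% to 47%, and an unrecorded treatment change could push it the other way. The problem is confined to late samplers, but in a single-arm study of 12, three of them are a quarter of the data. It should be corrected because it touches the primary outcome and costs little to remove.

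**What to change.** 1. Require the week 16 stool on or before the day the device is returned.
2. If it has not been collected by Visit 4, let the subject keep the device, continue 3 sets a day, and return it once the stool is collected, by day 119 at the latest. Amend Visit 4, item 7 to match.
3. Record the stool date, the date of last stimulation, and any Crohn's medication change up to the stool date.
4. Give one stool window per time point: days 49–63 for week 8 and days 105–119 for week 16.
5. Keep ± 5 days for Visits 3 and 4, and delete the ± 1 week bracket from the two diary items.

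The off-device interval before the stool then becomes 0 days. The cost is wording in the two stool items, the two diary items and Visit 4, item 7, plus the recording in step 3; no clinic visit is added. The drawback is that a few subjects would stimulate some days longer and have to return the device separately. Simply requiring the stool by Visit 4 also removes the off-treatment sample, but leaves no way to obtain an on-treatment value from a subject who misses that deadline.

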Materials and Methods: Adult patients with Crohn's disease presenting to the Indiana University Medical center will be invited to participate in the study. Additionally, potential participants can receive information about participation at disease specific health fairs, and educational event.

Ages Eligible for Study: 18 to 75 Years, inclusive.

Sexes Eligible for Study: All

Inclusion Criteria:

1. Crohn's disease diagnosis for at least 3 months, confirmed by clinical, biochemical, and endoscopic evaluations.
2. Patients with CD involving the small bowel and / or colon with active symptoms with Crohn's Disease Activity Index (CDAI) > 220 despite at least one conventional therapy (corticosteroids and/or immunosuppressives) with a stable dose will be included.
3. Elevated Fecal calprotectin ≥ 200 $\mu\text{g/g}$ within the past 4 weeks prior to enrollment
4. If on corticosteroids, the dose must be stable and $\leq 20\text{mg/day}$ prednisone or equivalent for at least 14 days before entry into study.
5. If on background immunosuppressive treatment the dose must be stable with the following parameters:

6. 56 days (8 weeks) for Immunomodulators (methotrexate, 6-MP, Azathioprine) and small molecules (upadacitinib)
7. 84 days (12 weeks) for biologics (Infliximab, Adalimumab, Vedolizumab, Ustekinumab, Risankizumab)
8. Clinical laboratory evaluations (including a chemistry panel, complete blood count [CBC], and urinalysis [UA]) within the reference range for the test laboratory, unless a typical consequence of CD or deemed not clinically significant by the Investigator. Labs done clinically within the past 30 days will be used for this criterion and will not need to be repeated for inclusion in the study.
9. Colonoscopy within the previous 1 year with no evidence of colonic dysplasia or cancer.
10. Able and willing to give written informed consent and comply with the requirements of the study protocol.

Exclusion Criteria:

1. Expectation to increase corticosteroids and/or immunosuppressive treatment
2. Presence of bowel stricture with pre-stenotic dilatation
3. Presence of intra-abdominal or perirectal abscess
4. Crohn's Disease Activity Index (CDAI) < 220
5. Fistula with clinical or radiological evidence of abscess
6. Perianal CD with or without rectal involvement
7. Ileostomy, colostomy, enteral or parenteral feeding
8. Short gut syndrome.

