shared with Purdue University Laboratories for analysis. No subject identifiers will be shared. Samples will be de-identified per HIPAA standards. Only the research study team will have access to the identification key and sample storage. Subjects will not be able to obtain future access to the stored biospecimens for information that may be of clinically relevant to him/her.

If a subject chooses to withdraw from the study, the investigators will continue to use data already collected up to the point of withdrawal. Biospecimens will be kept, and all personal identifiers removed upon withdrawal.

There will be no whole genome sequencing of the samples. These specimens will not be used for commercial profit.

Study Funding: The study devices for transcutaneous vagal nerve stimulation will be obtained through a grant from the manufacturer GammaCore; ElectroCore Inc.; Rockaway, NJ, USA. Study procedures involving stool calprotectin assay, cytokine assays and electrocardiograms will be funded by the Indiana University Division of Gastroenterology

References:

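### No stool calprotectin is planned when a subject is withdrawn for flare or medication change, so the primary outcome loses week-16 values for reasons probably linked to disease activity

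*Protocol*

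**What the plan says.** Under Outcome Measures, the primary outcome is "Change in fecal calprotectin over time [16 weeks"], in a single-center, open-label study of an estimated 12 participants.

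Under Study Withdrawal/Discontinuation there are two rules:
- Flare: "If a subject experience a Crohn's disease flare they will be withdrawn from the study and considered a non-responder".
- Medication change: "If the subject changes their Crohn's disease medication they will be withdrawn from the study".

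Post-baseline stool is planned at two points only. The section for weeks 1-7 says "Stool for week 8 can be collected within a week of Visit 3 (Week 8 +/- 1 week"), and the section for weeks 8-15 says "Stool for week 16 can be collected within a week of Visit 4 (Week 16 +/- 1week"). The CDAI diaries are likewise handed in at Visits 3 and 4; for the second half the wording is "During weeks 8-15 to be collected at Visit 4 (Week 16 +/- 1week").

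Additional Research Collection says that, when a subject chooses to leave, "the investigators will continue to use data already collected up to the point of withdrawal". Neither the visit descriptions nor the withdrawal section mentions an early-termination visit, a sample at withdrawal or follow-up afterwards. For a withdrawal by the investigator, the protocol requires only that the withdrawal and its reason be documented.

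**The concern.** The two withdrawal triggers are a worsening of the disease, and a change in its treatment that will often follow from disease activity. The primary outcome measures inflammation from that same disease. The subjects who lose their week-16 value are therefore likely to differ, in the very quantity being measured, from those who keep it.

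There is no control arm in which similar losses might offset this, and each subject is 1/12, or about 8%, of the sample. If those who worsen drop out of the 16-week mean, the mean of those who remain tends to show improvement even if stimulation does nothing.

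This is a matter of data collection. An analysis plan can decide how to use the values it has, but it cannot supply one that the protocol never asked for.

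**Working it through.** **Timing, from the protocol.** Week 8 is day 56 and the stool window is 1 week either side, so the earliest planned post-baseline stool is at about day 56 - 7 = 49. Week 16 is day 112, and 49/112 = 44% of follow-up.
- Withdrawal before about day 49: no planned post-baseline calprotectin.
- Withdrawal after the week-8 sample and before the final one: the week-8 value is kept, but there is no planned week-16 value.

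**Size, illustration only.** The protocol gives no flare rate, SD, correlation or basis for the 12, so it has no figure to reproduce. Assumptions:
- the true mean log change is 0;
- the SD of log change is 0.9;
- the correlation r between a latent flare tendency and the week-16 change is 0.5 to 0.7;
- those with the highest flare tendency are withdrawn, before any week-8 stool.

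Shift in completers' mean log change = -(sum of the withdrawn subjects' expected flare scores / number of completers) x r x SD. The percentage change is exp(shift) - 1. The interval rates below come from 200,000 simulated trials.

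*One of 12 withdrawn.* The largest of 12 standard normal values averages 1.629, and 1.629/11 = 0.148.
- r = 0.5: 0.148 x 0.5 x 0.9 = 0.067, a fall of 6%.
- r = 0.7: 0.148 x 0.7 x 0.9 = 0.093, a fall of 9%.
- A 95% t interval lies wholly below no change in 4-6% of trials, against 2.5% with all 12 observed.

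*Three of 12 withdrawn, all for worsening (extreme case).* The three largest scores sum to 3.54, and 3.54/9 = 0.393.
- r = 0.5: 0.393 x 0.5 x 0.9 = 0.177, a fall of 16%.
- r = 0.7: 0.393 x 0.7 x 0.9 = 0.248, a fall of 22%.
- The interval lies wholly below no change in 8-14% of trials.
- The completers' standard error is about 0.27 and 0.26, so the shift is 0.177/0.27 = 0.66 to 0.248/0.26 = 0.95 standard errors. It is within sampling error.

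*Two withdrawn for worsening and one after improvement.* The fall is 5-8%. At r = 0 it is nil.

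**Effect of a retained week-8 value, carried forward in the three-withdrawal case.** The answer depends on how closely the week-8 change tracks flare tendency.
- If it does so only through the week-16 change, its correlation with flare tendency is 0.5 x 0.5 = 0.25 to 0.7 x 0.7 = 0.49. The spurious fall is then 12-17%, 8-13% or 4-9% when one, two or all three have a week-8 value.
- If it tracks flare tendency as closely as week 16 does, the fall is 10-14%, 5-7% or 0%.

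**Effect of a withdrawal sample for all three.** If it tracks flare tendency as week 16 would, the bias is 0, but that is true by construction. If its correlation is 0.2 lower or higher, the shift is 0.9 x 0.2 x 3.54/12 = 0.053, or about 5% either way.

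**The case against.** The best case against acting is that the protocol already limits the problem. It requires stable doses and excludes subjects with "Expectation to increase corticosteroids and/or immunosuppressive treatment". It has a mid-study stool, and it keeps data gathered before a subject chooses to leave. It is a pilot of 12 with no stated test, alpha or success criterion, so there is no formal error rate to inflate. A stool taken at flare is off schedule, may catch the disease at its worst, and could bias the mean the other way.

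Much of this stands. The eligibility rules make medication changes less likely. They do not exclude flares, because subjects enter with CDAI above 220 despite conventional therapy. The week-8 value helps those who reach it. The interval rates rest on an assumed t interval and only show scale. The off-schedule point is fair, and is why the result should be shown both ways.

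A reader might go further in four directions that the protocol does not support:
- *The result will be biased towards benefit.* Withdrawal for a reduction in medication after improvement would act the other way, and the protocol gives no rates.
- *Withdrawn subjects contribute nothing.* A week-8 value still counts in a change over time.
- *The non-responder label contradicts the outcome list.* The listed efficacy outcomes are changes in measured quantities, but a subject can be classed as a non-responder alongside them. A response cut-off and its analysis may be left to an analysis plan that is not shown.
- *The CDAI diaries are lost.* Naming Visits 3 and 4 as hand-in points does not bar earlier retrieval; the protocol simply does not ask for it.

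**Conclusion.** The concern holds as a gap in data collection. Followed as written, the protocol withdraws subjects for flare or medication change and plans no calprotectin at that moment. Week-16 primary values, and for early withdrawals all planned post-baseline values, are then lost for reasons probably linked to the outcome.

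The likely effect is a more favourable 16-week change. Under the assumed null effect, log SD of 0.9 and correlation of 0.5-0.7, it is 6-9% with one early withdrawal. The 16-22% figure needs three early withdrawals, all for worsening, and should not be read as the expected case. Retained week-8 values could reduce the bias by anything from a small part to all of it. None of these inputs comes from the protocol.

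This should be fixed because the remedy is cheap and the sample cannot be obtained afterwards. It is not a flaw that invalidates the study.

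**What to change.** Leave the clinical withdrawal rule to the sponsor and add the following to the protocol.
- At withdrawal for flare or medication change, request a stool calprotectin by the existing collection route and retrieve the CDAI diaries. Do this where possible before new medication takes effect, and without delaying treatment. The withdrawal itself is the trigger.
- Record the date and reason with each such value. Use these values, with any week-8 value, in the analysis of change over time, and show the result with and without them because they are off schedule.
- Keep flare withdrawals, which the protocol already calls non-responders, in the denominator of any response summary. The cut-off and the handling of medication-change withdrawals can be left to the analysis plan.

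The cost is one stool sample and a diary return per withdrawn subject, a protocol amendment with IRB submission, and probably a less favourable estimate. The sample reduces the bias to the extent that it reflects what week 16 would have shown; it cannot be promised to remove it.
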